EEG/ERP recording: subjects will be asked to wear a cap containing electrodes. Electrode paste will be used to facilitate the connection. Subjects may listen to sound stimulations by wearing a pair of headphones, hearing tubes, or through loudspeakers. Tests may include resting EEG, passive and active cognitive tasks. In resting EEG, subjects are asked to relax during brain wave recording. In brain wave recording during passive task: subjects may be asked to relax while sounds at different frequencies and durations are presented to elicit evoked potentials, which can be accompanied by visual presentations. No performance is required except to be alert. In brain wave recording for attention and memory tasks: subjects are asked to pay attention to auditory and visual stimuli while holding a response pad. They are trained and then perform the tasks by responding, remembering, or recalling certain items and ignoring the other items. These tasks are computerized auditory and visual stimuli and data are digitally recorded. Each test may last a few minutes to about half an hour; they are repetitive but with breaks between tasks to reduce subject fatigue. All recordings are stored in secure servers/computers using only a code.

TMS will be given in 2 sessions in 2 different days that are separated by one or more days. In one session you will receive active TMS. In another session you will receive sham TMS. The active or the sham TMS are delivered to one, two or three locations on your scalp. The TMS is given in about 4 minutes for each location. Therefore, in the active TMS day, you will receive 3 TMS administrations in three locations, one after another, for a total of about 12 minutes. In the sham TMS session, you may feel or hear similar TMS, but no actual TMS is stimulating your brain. TMS-evoked responses, brain waves, and MRI will be measured before and after each session to determine the TMS effects. It will take about 4 to 5 hours. It includes about 2 hours before and 2 hours after the TMS where we will perform clinical assessments, TMS-evoked responses, brain wave, and MRI assessments as described above. It also includes time to wear the electrode cap and remove the electrode cap and cleaning the hair after the experiment. About 30 participants will participate in this study.

Research Related Risks

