Brain wave recording: A paste is used to attach the electrodes during brain wave testing, which may irritate the skin on the scalp or face. Irritation is mild and usually resolves quickly. We may ask you to not use hair products on the day of testing (or it has to be washed out prior to testing, which may be inconvenient). The electrode cap you wear can be tight and not comfortable, but it can be adjusted. The tasks can be quite long, boring, or even annoying. Some of the sounds can be loud and uncomfortable. We will give frequent breaks in-between. You can always ask for a break or re-schedule for another time to complete the study.

All safety measures to lessen any side effects will be taken. If you feel that you want to leave the study, you are free to do so at any time. If we feel that you should not continue, we will end the study. We may do this even if you do not want to end the study.

Because TMS is relatively new, its long-term effects are still unknown. We will monitor you at every visit. There may be risks in this study which are not yet known. You will be told of any new findings during the course of this study that may affect your participation. If you feel that you have an illness or symptoms related to your being in the study you should call us.

Statistical Analysis Plan

Demographics were compared using ANOVA or χ^2 tests. We will examine the differences in performances of biomarkers in active TMS compared to sham TMS. We will explore effects of age, sex, baseline medication, cognition, smoking status, and functional measures on biomarkers, and significant findings will be included as covariates. Exploratory analyses were conducted comparing active TMS vs. sham at different time points using independent-sample t-test and comparing baseline vs. post-TMS measurements using paired-sample t-tests at $p < 0.05$. Effect sizes were calculated for nominally significant measures using Cohen's d. All tests were two-tailed.

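### The SAP names no test comparing the active-day change with the sham-day change, although both sessions are measured before and after stimulation

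*Combined protocol and SAP*

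**What the plan says.** The Statistical Analysis Plan opens its comparison of conditions with a general aim: "We will examine the differences in performances of biomarkers in active TMS compared to sham TMS". It attaches no model, contrast or test to that aim.

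The named tests come in one later sentence. It begins "Exploratory analyses were conducted comparing active TMS vs. sham at different time points using independent-sample t-test" and goes on to "comparing baseline vs. post-TMS measurements using paired-sample t-tests" at p < 0.05. The plan adds "All tests were two-tailed". It does not say whether the paired tests are run in the active session, the sham session or both. Cohen's d is to be calculated only for measures that reach nominal significance.

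Under Study Procedures, the paragraph on the TMS sessions gives each participant one active and one sham session on different days. TMS-evoked responses, brain waves and MRI are recorded before and after each. A session takes about 4 to 5 hours: "It includes about 2 hours before and 2 hours after the TMS". About 30 participants are planned. The order of the two sessions is not stated.

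On the test burden, the EEG/ERP recording paragraph says of the tests that "they are repetitive but with breaks between tasks to reduce subject fatigue". The brain wave paragraph under Research Related Risks says "The tasks can be quite long, boring, or even annoying".

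**The concern.** The study hypothesis is that TMS improves oscillations, cognition and circuit measures. A change from before to after one session mixes any such effect with whatever else happens over several hours of repeated testing. Practice can look like improvement. Fatigue can look like worsening, or can hide a benefit. The sham day repeats the same battery in the same people and is the natural reference for this drift, yet neither named test uses it to adjust a change.

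The two named tests fail in opposite directions. The paired test is exposed to drift. The independent-sample test is protected from drift common to both days, but it discards the pairing and so has little chance of reaching significance. Nominally significant results would therefore tend to come from the test that cannot attribute them to TMS, and those are the results for which an effect size is then calculated.

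**Working it through.** The documents give no power, SD or effect size, so there is no planned figure to reproduce.

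**Inputs from the documents:** n = 30 (about 30 planned), two-sided alpha 0.05, paired t-test, two sessions per participant with a measurement before and after each.

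**Assumptions, not in the documents:** no TMS effect; the same drift *d* on both days, in units of the SD of the pre-to-post change; for the simulations, equal correlation of 0.3, 0.5 or 0.7 among a participant's four measurements, and no order or carryover effect.

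**Step 1: one-session paired test.** The statistic is noncentral t with 29 degrees of freedom and noncentrality d√30; the critical value is 2.045.

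| Drift d | d√30 | Probability of p < 0.05 |
|---|---|---|
| 0 | 0 | 5.0% |
| 0.1 | 0.548 | 8.3% |
| 0.2 | 1.095 | 18.5% |
| 0.3 | 1.643 | 35.5% |
| 0.5 | 2.739 | 75.4% |

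**Step 2: independent-sample active versus sham test at the post time point.** Drift common to both days cancels in the difference of means. In 40,000 simulated trials per scenario, the test rejected in about 2%, 0.7% and 0.07% of trials at correlation 0.3, 0.5 and 0.7, with or without drift. It falls below 5% because its standard error ignores the positive correlation between a participant's two sessions.

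**Step 3: the missing contrast.** Take (active post − active pre) − (sham post − sham pre) for each participant and apply a one-sample t-test. In the same simulations it rejected in 4.8% to 5.1% of trials in every scenario (drift 0 to 0.5, correlation 0.3 to 0.7).

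**Step 4: what the contrast costs.** If the two changes are uncorrelated with equal SD, the contrast has √2 times the SD of one change. For a true effect of 0.5 SD of the change and no drift, the standardised effect falls to 0.5/√2 = 0.354 and power is 46.5%, against 75.4% for the one-session test. A drift of 0.5 with no TMS effect also gives that test 75.4%.

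**Step 5: what the contrast does not remove.** Suppose everyone has the same session order and drift falls from 0.5 on the first day to 0.2 on the second. The contrast then carries a bias of 0.3 SD of the change, which standardises to 0.3/√2 = 0.212. It rejects in about 20% of trials with no TMS effect.

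**Step 6: choice of model.** A session-by-time term with only a participant random intercept is not interchangeable with the contrast. With day-to-day variance equal to residual variance (assumed), it rejected in about 1.2% of simulated null trials, against 4.8% for the contrast.

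**The case against.** The strongest reply is that the plan has a sham control and puts it first. Its lead comparison is active against sham, sham data are collected in every participant, and the paired tests are labelled exploratory. All of this stands. A reader might infer that the plan has no sham reference, or that it will rest its claim on uncontrolled pre/post tests. The documents support neither: no section says that an effect will be claimed from a paired result, and the active versus sham test is not inflated by drift common to both days (Step 2). The error arises only if a paired result is interpreted alone.

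A reader might also infer that the plan will treat significance after active but not after sham as evidence. No such rule is stated. It would be a poor one: with drift of 0.3 and independent sessions it would be met in 0.355 × 0.645 = 23% of trials with no TMS effect. That is a warning about a possible misreading, not a defect in the text.

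The evidence for drift is also two-sided. Breaks are planned, training before the attention and memory tasks could reduce later practice gains, and the learning tasks in the MRI list are optional, with each participant doing a subset. The size of any drift is unknown, and at 0.1 SD the rate is only 8.3%.

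What remains is that no named test makes the comparison for which the design supplies the data, and nothing rules out reading a one-session change alone.

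**Conclusion.** The point holds as a gap in specification. The sham-controlled comparison is stated as an aim without a test. Of the two tests that are named, one has no sham term and the other ignores that the same participants receive both conditions. Neither compares the change on the active day with the change on the sham day.

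The inflation to between 8.3% and 75.4% is conditional. It applies to a one-session paired test read alone as a TMS effect, with 30 participants and an assumed drift of 0.1 to 0.5 SD of the change. With no drift the test keeps its 5%. The absence of the contrast from the SAP is certain; the amount of drift in this study cannot be learned from the documents. Because the tests are exploratory and the remedy is wording, this is a change that should be made, not a flaw that invalidates the study.

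**What to change.** For each biomarker, state that the test of a TMS effect is the within-participant contrast (active post minus active pre) minus (sham post minus sham pre), and drop the independent-sample test for this purpose. Two forms are suitable:

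- a paired t-test of the two changes, extended to a regression of the contrast on session order (coded +1 and −1), whose intercept is the order-adjusted TMS effect; or
- a mixed model for the four measurements with a condition-by-time term, random effects for participant and for session within participant, and session order included. The order term must include day-by-time, because a constant difference between days already cancels in the contrast.

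State the session order and whether it is balanced. If everyone has the same order, no model can separate order from condition, and the report should say so. Say which participants enter each analysis: the MRI procedures section allows people to stay in the study with some tests incomplete, so the simple contrast needs all four measurements for that biomarker.

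Report pre-to-post changes for both sessions as descriptive results. Add a sentence that no TMS effect will be claimed from a change in the active session alone.

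The analysis change is SAP wording only and needs no new measurements. The price is precision: the contrast is noisier than a single change (46.5% against 75.4% power in Step 4), so fewer measures will reach p < 0.05. It removes only drift common to both days; if order is not already balanced, balancing it is a change to the conduct of the study.

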MRI procedures: MRI will be done in a 3.0 Tesla magnet. During MRI, the subjects will perform resting and behavioral and cognitive tasks with visual and auditory presentations to be shown through a screen and head/ear phones. In some tasks the subject will be asked to simply rest, or to use a response pad. The specific tasks may include structural images for gray and white matter, resting scan, tasks that measure eye movement, motion perception and prediction, attention/working memory, learning and reversal learning tasks, finger tapping, and/or simple auditory and visual stimulus tasks. Each subject will perform only a subset of these tasks. Behavioral response, eye movement, basic physiological measures including breath, blood pressure, pulse, skin conductance can be recorded during imaging. Each subject will be inside the scanner for about 1 hour at different time of the rTMS treatment procedure. About four fMRI scans will be done in each sub-study. A repeat of scan is possible if other issues have led to incomplete or poor quality imaging data in previous scans. If a participant is not sure whether there are metal in their head or eye, for example past gunshot wound or involving in welding or metal drilling without eye protection, we may ask the participant to have a head x-ray of the head to make sure there is no metal in eyes or head before the MRI scan. The x-ray will involve a small amount of radiation, although the risk associated with a one-time x-ray is similar to any x-ray a doctor may prescribe during a clinic visit. They can refuse the x-ray and not participate in the MRI portion of the study. We may use some clinical assessments such as SCID done in other studies or previous clinical assessments if repeating them is not necessary. Similarly, data

collected here may be combined with data from other studies when appropriate. Data collected from this study may be combined with other related studies (e.g., brain imaging data collected from other protocols where combining data is stated) during data analyses. Subjects may not necessarily be excluded or withdrawn if they complete some but not all of the tests and assessments although we encourage them to complete all tasks.

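### Cohen's d is planned for nominally significant measures and no others; at about 30 participants this overstates small effects on average, and moderate ones under the planned tests

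*Combined protocol and SAP*

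**What the plan says.** The Statistical Analysis Plan describes two exploratory sets of t-tests. The first is the treatment contrast: "Exploratory analyses were conducted comparing active TMS vs. sham at different time points using independent-sample t-test". The second compares baseline with post-TMS values by paired t-test at the 0.05 level. On sidedness it states: "All tests were two-tailed". Between these comes the reporting rule: "Effect sizes were calculated for nominally significant measures", with Cohen's d as the measure. The plan mentions no other effect size, and no confidence interval for any measure. It does not say which standard deviation d is divided by.

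Two facts from Study Procedures fix the scale of the problem. The design is within-participant: "In one session you will receive active TMS. In another session you will receive sham TMS". The size is given as "About 30 participants will participate in this study".

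**The concern.** If d is calculated when p<0.05 and not otherwise, the p-value decides which estimates are seen. For a given test and sample size, p<0.05 is the same as |t| exceeding a fixed value, and so (where d is built from the same t) as |d| exceeding a fixed value. Estimates that fall low by chance are dropped and those that fall high are kept, so the average of the reported values lies above the true effect. The bias is worst where power is low, which at about 30 participants means small effects, and moderate ones to a lesser degree.

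What is at stake is how the size of TMS effects on the biomarkers is described. Reported d values would be too large on average for small and moderate effects. Measures that miss p<0.05 would have no planned d beside them, so biomarkers could not be set on one effect-size scale unless d were recomputed from means and SDs, or from t and n. The plan neither promises nor withholds those figures.

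**Working it through.** **Inputs from the documents.** n = about 30, each participant with both sessions (Study Procedures); two-sided 0.05; independent-sample test for active versus sham and paired test for baseline versus post (Statistical Analysis Plan). The documents contain no power calculation, effect size or SD, so there is no figure of the plan's own to reproduce.

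**Assumptions.** True effect δ of 0.3, 0.5 or 0.8; correlation between a participant's two sessions of 0, 0.5 or 0.7; normal data; 30 participants contributing to each measure. For active versus sham, d is the mean difference divided by the pooled SD. For baseline versus post, d is the mean change divided by the SD of change. These are different scales, so an effect of 0.3 on one is not an effect of 0.3 on the other, and the two sets of results should not be compared.

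**Step 1: smallest d that can be reported.**

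- Independent test: t(0.975, 58) × √(2/30) = 2.002 × 0.2582 = 0.517.
- Paired test: t(0.975, 29) / √30 = 2.045 / 5.477 = 0.373.

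True active-versus-sham effects of 0.3 and 0.5 both lie below 0.517, so every reported d of the right sign overstates them.

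**Step 2: mean d given p<0.05, active versus sham, planned independent test.** Simulation of 200,000 trials per setting. Entries are for correlation 0 / 0.5 / 0.7.

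| True d | Share of measures given a d | Mean reported d | Mean d with no filter |
|---|---|---|---|
| 0.3 | 21% / 13% / 8% | 0.67 / 0.62 / 0.59 | 0.30 to 0.31 |
| 0.5 | 48% / 47% / 46% | 0.73 / 0.67 / 0.64 | 0.51 |
| 0.8 | 86% / 93% / 97% | 0.88 / 0.84 / 0.83 | 0.81 to 0.82 |

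At correlation 0 the exact noncentral t (noncentrality δ√(n/2), 58 df) gives the same means: 0.67, 0.73 and 0.88. As ratios to the truth, 0.3 is overstated 2.0 to 2.2 times (0.594/0.3 to 0.666/0.3) and 0.5 is overstated 1.3 to 1.5 times (0.643/0.5 to 0.728/0.5).

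**Step 3: baseline versus post, paired test.** Numerical integration of the noncentral t (noncentrality δ√n, 29 df).

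| True d | Share given a d | Mean reported d | Mean d with no filter |
|---|---|---|---|
| 0.3 | 36% | 0.51 | 0.31 |
| 0.5 | 75% | 0.59 | 0.51 |
| 0.8 | 99% | 0.83 | 0.82 |

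**Step 4: how much of Step 2 comes from the choice of test.** The same pooled-SD d for active versus sham, but filtered on a paired test, at correlation 0 / 0.5 / 0.7:

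- true 0.3: 0.66 / 0.50 / 0.41
- true 0.5: 0.73 / 0.58 / 0.53
- true 0.8: 0.88 / 0.82 / 0.82

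The SD of a difference is about SD × √(2(1 − ρ)), where ρ is the correlation. The paired cut-off in pooled-SD units is therefore about 0.373 × √2 = 0.53 at ρ = 0 and 0.373 × √0.6 = 0.29 at ρ = 0.7. At ρ = 0 a paired filter gains nothing. At ρ = 0.7 it removes 0.594 − 0.410 = 0.18 of an inflation of 0.594 − 0.307 = 0.29 for true 0.3, and 0.643 − 0.530 = 0.11 of 0.643 − 0.510 = 0.13 for true 0.5.

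**The case against.** The strongest reply is that the plan labels these analyses exploratory and the results nominal, so readers know how measures were chosen; that it never says d is withheld elsewhere; and that d can be recovered from ordinary summary statistics. Part of this stands. The label properly limits what the p-values can support, and that no other measure gets a d is inferred from the single class named and the absence of any other estimate. But a label does not shift a biased average, and the plan does not commit to the statistics from which d could be rebuilt.

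A second reply is that the larger fault in the active-versus-sham contrast is the independent-sample test applied to two-session data. That is largely right when the sessions are correlated, as Step 4 shows. It does not dispose of the point: small effects remain inflated under a paired filter (0.41 for true 0.3 at correlation 0.7), and the baseline-versus-post contrast, where the test does match the design, still turns 0.3 into 0.51.

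A reader might also infer more than the documents support:

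- *That large effects become seriously inflated once fewer participants have a measure.* The MRI procedures section says "Each subject will perform only a subset of these tasks", but this concerns MRI tasks and gives no number. With 20 participants assumed, a true 0.8 averages 0.89 to 0.98 under the independent test. Under the paired test it averages 0.87 against 0.83 unfiltered, so the filter adds only about 0.04.
- *That moderate effects are materially biased under any test.* With a paired filter at correlation 0.7, true 0.5 averages 0.53 against 0.51 unfiltered.
- *That a later treatment study would be planned on inflated effects.* The Background section places treatment development outside this protocol, so that use is hypothetical.

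**Conclusion.** The point holds as a minor reporting matter. Followed as written, the rule produces d values that overstate small effects on average under every test considered, and moderate effects under the tests the plan names. Large effects (0.8) are little affected at 30 participants: 0.83 to 0.88 across the planned tests.

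The sizes rest on assumed true effects, an assumed correlation of 0 to 0.7, normal data, about 30 participants per measure and the standardisers stated above. The direction of the bias for small effects does not depend on where in that range the truth lies. Much of the active-versus-sham inflation belongs to the independent-sample test when sessions are correlated, and the share depends on a correlation the documents do not give. The p-values and test decisions are not affected by the reporting rule.

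**What to change.** Replace the effect-size sentence in the Statistical Analysis Plan with:

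> For every biomarker, contrast and time point tested, whatever its p-value, the mean difference with 95% CI and Cohen's d with 95% CI will be reported, with the standardiser stated and the same for all measures within a contrast, and with CIs computed from within-participant differences where each participant contributes both values.

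The standardiser has to be named because otherwise the d values may still not share a scale. The interval has to use within-participant differences because an independent-sample interval would ignore the two-session pairing. With every measure reported, mean d falls within about 3% of the truth at 30 participants, which is ordinary small-sample bias.

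The cost is one sentence and longer tables. No additional data, participants or procedures are needed.
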